10.2 Sample Size and Accrual

12 subjects allows 80% power to detect a reduction in skin test positivity rate from 100% before treatment to 15% after treatment using a one-sided 0.05 level McNemar's test. Patients will be recruited from the allergy clinics at Northwestern University Feinberg School of Medicine with a diagnosis of peanut (or tree nut) allergy by a board certified allergist-immunologist.

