for toxicities (see below). After this visit, subjects will be given ibrutinib (two doses of 420 mg of ibrutinib to start the following day and to be taken orally at 8am exactly 24 hours apart) and return for **Visit 2** to undergo repeat PST and phlebotomy for testing preformed in an identical manner to Visit 1. If two consecutive doses of 420 mg of ibrutinib given 24 hours apart is insufficient to cause >80% inhibition of the SPT and BAT response, subjects will be given two additional doses of 420 mg of ibrutinib to continue to take at 8am exactly 24 hours apart for two more days, and return for **Visit 3** for identical repeat testing as in Visits 1 and 2. If four consecutive doses of 420 mg of ibrutinib given 24 hours apart is insufficient to cause >80% inhibition of the SPT and BAT response, subjects will be given three additional doses of 420 mg of ibrutinib to continue to take 24 hours apart for three more days, and return for **Visit 4** for identical repeat testing as in Visits 1, 2 and 3, where based on preliminary data, we expect SPT and BAT to be suppressed. Once both the SPT and BAT responses are inhibited, no further ibrutinib doses will be given, and subjects will return on a weekly basis until both the peanut/tree nut PST and BAT return to at least 80% of baseline values. At this point, Part 1 will have been completed. At each visit, patients will be monitored for toxicities, including CBC, CMP, and pregnancy testing. Prior to drug initiation and at the end of the trial, an EKG will be performed.

Clinical protocol for part 1 (top) and part 2 (bottom). * or - = predicted response; ??? = question to be answered; * = if needed

and subjects will return on a weekly basis until both the peanut/tree nut PST and BAT return to at least 80% of baseline values. At this point, Part 1 will have been completed. At each visit, patients will be monitored for toxicities, including CBC, CMP, and pregnancy testing. Prior to drug initiation and at the end of the trial, an EKG will be performed.

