3.1 Inclusion Criteria

- 3.1.1 History of food allergy to peanut (or tree nut).
- 3.1.2 Male or female age \geq 18 years.
- 3.1.3 Positive skin prick testing and basophil activation test to the trigger food(s), either peanut and/or tree nut(s).
- 3.1.4 Clinical reaction to oral food challenge at baseline (for Part 2 only)
- 3.1.5 Adequate organ and marrow function as defined below:

- leukocytes	\geq 3,000/mcL
- absolute neutrophil count	\geq 1,500/mcL
- platelets	\geq 100,000/mcL
- total bilirubin	within normal institutional limits
- AST(SGOT)/ALT(SPGT)	within normal institutional limits
- Creatinine	within normal institutional limits
- 3.1.6 Women of child bearing potential must agree to two forms of highly effective contraception (hormonal, device, or barrier method of birth control; abstinence) prior to study entry, for the duration of study participation, and for 90 days following completion of therapy. Should a woman become pregnant or suspect she is pregnant while participating in this study, she should inform the Principal Investigator and her treating physician immediately.
 - 3.1.5.1 A female of child bearing potential is any woman (regardless of sexual orientation, having undergone a tubal ligation, or remaining celibate by choice) who meets the following criteria:
 - Has not undergone a hysterectomy or bilateral oophorectomy; or
 - Has not been naturally postmenopausal for at least 12 consecutive months (i.e., has had menses at any time in the preceding 12 consecutive months).
- 3.1.7 Ability to understand and the willingness to sign a written informed consent.
- 3.1.8 Ability to clearly understand and speak English at an 8th grade reading level. For safety reasons, subjects must speak English due to the anticipated need for clear and timely communication with investigators and the study team in emergency situations, since the investigators and study team are English speaking.

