4.0 TREATMENT PLAN

4.1 Treatment Dosage and Administration

For Part 1 of the study, we will determine the length of treatment (i.e., the number of daily doses) required to inhibit both basophil and food skin test responses. Preliminary data demonstrates that 7 days of treatment will inhibit both basophil and mast cell responsiveness to aeroallergens, but have not yet tested shorter time points. Prior studies in cancer subjects suggest that one dose is sufficient to completely inhibit BAT, but we propose a minimum of two doses to allow for diffusion and penetration of ibrutinib into the skin compartment where our SPT is performed to assess skin mast cell responsiveness. For Part 1, 6 subjects will take ibrutinib 420 mg, by mouth once daily (every 24 hours) on an outpatient basis. After two days, the subject will undergo blood testing and SPT to assess basophil and mast cell reactivity. If both tests are negative, Part 1 is completed. If both tests are not negative, then the subject will take 2 more days of ibrutinib (same dose, for a total of 4 doses), and identical testing will be repeated. If testing is not negative at day 4, the subject will take 3 more days of ibrutinib (same dose, for a total of 7 doses), which is the maximum anticipated number of doses needed to suppress both the BAT and SPT.

For Part 2 of the study, 6 subjects will take ibrutinib 560 mg once daily by mouth (every 24 hours) for 2 days, which is the minimum number of days required to cause $\geq 80\%$ inhibition of food SPT and BAT responses as determined in part 1. Part 2 will last a minimum of 3 days.

Dose-limiting toxicity (DLT) includes any grade 3 or 4 hematologic toxicity, grade 3 hepatotoxicity or increase in creatinine $\times 2.5$ normal limit. DLT will be monitored at each visit, at any time during treatment.

Maximally tolerated dose (MTD) will occur at the point DLT occurs. Ibrutinib is approved as a daily medication for another indication, and we propose to use the drug in adults only at its approved oral dosing of 420 or 560 mg daily for a minimum of two days and a maximum of 7 days. Dose limiting events include grade 3 or 4 hematologic events, grade 3 or 4 hepatotoxicity, AST or ALT >3 times normal range, creatinine >2.5 times normal range. DLT evaluation will be completed throughout the study, anytime during treatment.

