10.0 STATISTICAL CONSIDERATIONS

Descriptive statistics will be completed to determine an 80% reduction in skin prick wheal size and basophil activation test reactivity (as determined by % inhibition of anti-IgE-induced CD63 expression). As this is an open label study, each patient's responsiveness will be examined compared to themselves prior to initiation of treatment.

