10.3 Data Analyses Plans

As this is an open label trial, descriptive statistics will be used. Each patient will be compared to him/herself prior to beginning treatment and at each time point in the study to assess SPT size (parts 1 and 2), BAT response (parts 1 and 2), and OFC threshold and response (part 2).

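### The power figure in section 10.2 is wrong: with 12 subjects, a fall from 100% to 15% has 99.99% power under the exact one-sided McNemar test, and no version of the test gives about 80%

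*Combined protocol and SAP*

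**What the plan says.** Section 10.2 is the only sample-size statement: "12 subjects allows 80% power to detect a reduction in skin test positivity rate from 100% before treatment to 15% after treatment", with a one-sided McNemar test at the 0.05 level. It does not say whether the test is exact or asymptotic, and it gives no allowance for dropout.

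Section 4.1 divides the 12 subjects between two regimens: "For Part 1, 6 subjects will take ibrutinib 420 mg, by mouth once daily" and "For Part 2 of the study, 6 subjects will take ibrutinib 560 mg once daily by mouth". Section 10.2 does not say whether the test pools them.

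Inclusion criterion 3.1.3 requires a positive skin prick test and a positive basophil activation test to the trigger food, so skin test positivity is 100% at entry.

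The outcome behind the 15% is described in different ways:

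- Section 4.1, Part 1: "If both tests are negative, Part 1 is completed".
- Study schema, Part 1: dosing continues if the doses so far are "insufficient to cause >80% inhibition of the SPT and BAT response".
- Section 10.0: "Descriptive statistics will be completed to determine an 80% reduction in skin prick wheal size".

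On analysis, section 10.3 says: "As this is an open label trial, descriptive statistics will be used". The McNemar test does not appear there.

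**The concern.** A fall from 100% to 15% is a very large paired effect, and all of the change is in one direction. A McNemar test on 12 pairs should detect it almost every time, so a stated power of 80% looks far too low.

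The error is in the safe direction, but it leaves the protocol without a sample-size justification that can be reproduced. A reader cannot recover 12 from the stated effect, and cannot tell whether 12 was meant for one pooled test or as 6 per regimen. The figure also hides what 12 subjects can detect, which is a much smaller effect than the one stated. Since the planned analysis is descriptive, the more useful property is the precision of an estimate from 6 or 12 subjects, and the plan does not give it.

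**Working it through.** **Inputs.** From section 10.2: n = 12, positivity 100% before and 15% after, one-sided α = 0.05, McNemar test. From criterion 3.1.3: everyone is positive at baseline. From section 4.1: 6 subjects per part.

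**Set-up.** Let b be the number of subjects who go from positive to negative, and c the number who go the other way. With all subjects positive at baseline, c = 0 and b ~ Binomial(n, 0.85), where 0.85 = 1 − 0.15.

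**Rejection rule, one-sided 0.05, c = 0.**

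- Exact: p = 0.5^b. b = 4 gives 0.0625 and b = 5 gives 0.031, so reject at b ≥ 5.
- Continuity-corrected: z = (b − 1)/√b. b = 5 gives z = 4/√5 = 1.79, p = 0.037, so reject at b ≥ 5.
- Mid-p: p = 0.5^(b+1). b = 4 gives 0.031, so reject at b ≥ 4.
- Uncorrected: z = √b. b = 3 gives z = 1.73, p = 0.042, so reject at b ≥ 3.
- Two-sided exact, for comparison: p = 2 × 0.5^b. b = 6 gives 0.031, so reject at b ≥ 6.

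**Attempt to reproduce the 80%.** Power = P(Bin(n, 0.85) ≥ cutoff). For the exact test with n = 12, P(b ≤ 4) = 0.0000717, so power = 1 − 0.0000717 = 0.99993.

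| Version | Cutoff | Power, n = 12 | Power, n = 6 | Smallest n with ≥ 80% | Still positive at 80% power, n = 12 |
|---|---|---|---|---|---|
| Exact, one-sided | 5 | 99.99% | 77.6% | 7 (92.6%) | 50% |
| Continuity-corrected, one-sided | 5 | 99.99% | 77.6% | 7 (92.6%) | 50% |
| Mid-p, one-sided | 4 | 99.9995% | 95.3% | 5 (83.5%) | 59% |
| Uncorrected, one-sided | 3 | 99.99997% | 99.4% | 4 (89.0%) | 68% |
| Exact, two-sided | 6 | 99.93% | 37.7% | 8 (89.5%) | 42% |

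The last column solves P(Bin(12, p) ≥ cutoff) = 0.80 for p and reports 1 − p. For the exact one-sided test p = 0.497, so 50.3% are still positive.

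**Other routes to 80% with n = 12.**

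- No cutoff on b gives it: b ≥ 9 gives 90.8% and b ≥ 10 gives 73.6%.
- The paired normal approximation gives 99.997% one-sided, and 99.13% in its most conservative form (two-sided, continuity-corrected).
- Baseline positivity of 90% to 99%, with an independent 15% afterwards, gives 97.8% to 99.95% (exact test).
- Losing subjects does not help: 7 to 11 evaluable subjects give 92.6% to 99.97% (exact test).

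The nearest matches come from n = 6, the size of one part: 77.6% with the exact one-sided test, and 77.9% with an uncorrected two-sided normal approximation. Neither is 80%, and section 10.2 says 12.

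**Precision.** Exact (Clopper-Pearson) 95% intervals for the proportion converted, at the counts nearest below the planned 85%:

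- one part, 5 of 6 (83%): 36% to 99.6%
- both parts, 10 of 12 (83%): 52% to 98%

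**The case against.** The strongest reply is that little depends on this. The error understates power, 12 subjects are ample for the stated effect, and the planned analyses are descriptive, so no conclusion would rest on the figure. This is fair. It limits the weight of the point and is why only wording needs to change.

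A second reply is that 80% may mean at least 80%. The sentence is then uninformative rather than false, but 12 still does not follow from it, because 7 subjects suffice under the exact test.

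A third is that a corrected figure above 99.9% could reassure too much. It assumes 15% still positive in both parts, and section 10.2 says only that this is after treatment. Section 1.2 reports that two 420 mg doses inhibit skin tests at least in part, and fully in only some cases. As an illustration, assume 70% still positive in Part 1 and 50% in Part 2 (assumed rates, not the protocol's). The chance of 5 or more conversions among 12 is then 56%. This part stands: a corrected power figure needs its time point and pooling stated, and a precision statement avoids the difficulty.

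On definitions, the schema and section 10.0 express much the same 80% criterion, and section 4.1 uses both a negative test and at least 80% inhibition. There are therefore three wordings but essentially two criteria. The gap remains, because a wheal can shrink by more than 80% without the test being negative.

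Section 10.2 also does not size the food-challenge endpoint of section 2.1. That is a separate matter and does not affect this one.

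**Conclusion.** The concern holds. Under section 10.2's own inputs the exact one-sided power is 99.99%, not 80%, and every version of the test examined exceeds 99% with 12 subjects. The result rests on 100% baseline positivity, which the entry criterion fixes, and on independent subjects with a common 85% conversion probability, which is the protocol's own assumption. Relaxing the baseline to 90% still leaves 97.8%.

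The documents do not show which input was misstated: the effect, the power, the test version or the number of subjects. A per-part origin is conjecture. The power arithmetic is certain. The missing definition of positivity, the unstated pooling and the absence of the test from section 10.3 are secondary, but they must be settled before any corrected figure can be reproduced. This should be fixed, but it does not threaten the adequacy of 12 subjects for the stated effect.

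**What to change.** Amend section 10.2 in one of two ways.

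(a) Keep the test and correct the figure, for example: *With an exact one-sided 0.05 McNemar test, 12 subjects pooled over Parts 1 and 2 give more than 99.9% power if skin test positivity falls from 100% to 15% (80% if it falls to about 50%); 6 subjects in one part give 78%.* State the time point and confirm that pooling is intended, then list the test in section 10.3.

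(b) Drop the test and state precision, for example: *If 5 of 6 subjects in one part convert, the exact 95% interval is 36% to 99.6%; for 10 of 12 over both parts it is 52% to 98%.* This fits the descriptive analysis already planned in section 10.3.

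In either case, state in section 10.2 which of the protocol's existing definitions of skin test response is meant. In section 10.3, report skin test conversion by part with exact binomial intervals at Visit 2, after two doses, which is the on-drug time point common to both parts. In Part 1, also report it cumulatively after 4 and 7 doses, because objective 2.2.2 asks for the minimum number of doses.

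The cost is wording in sections 10.2 and 10.3. Sample size, visits and data collection do not change.

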1.2 Study Drug Background and Associated Known Toxicities

Ibrutinib is a once daily, oral, selective, irreversible small-molecule inhibitor of Bruton's tyrosine kinase (BTK), a key component of B-cell receptor signaling (8,9). BTK is also essential for Fc ϵ RI signaling and triggering of mast cells and basophils (10){Iyer, 2011 #10272;Kuehn, 2008 #10273;MacGlashan, 2011 #8797}. It is currently FDA approved for the treatment of Mantle Cell Lymphoma (MCL), Chronic Lymphocytic Leukemia (CLL) and Waldenstrom's macroglobulinemia (WM).

In subjects with recurrent B-cell lymphoma, >90% irreversible occupancy of the BTK active site in peripheral blood mononuclear cells was observed up to 24 hours after ibrutinib doses of \geq 2.5 mg/kg/day. Ibrutinib is absorbed with a median Tmax of 1-2 hours. It is metabolized by cytochrome P450 and CYP3A, and has a half-life of 4-6 hours. The majority (80%) is fecally excreted.

The approved CLL and WM dose (420 mg orally once daily) has been shown to inhibit allergy test responses in cancer subjects receiving this drug by 1 week of treatment (the earliest time point examined) in preliminary data from our group. The 560 mg dose (used for MCL) has similar side-effect and toxicity profiles as the lower dose. Initial data from Part 1 suggests that the 420mg dose can at least partially (in some cases fully) inhibit skin test responses to peanut and tree nuts in allergic subjects after just 2 doses, with minimal side effects and no observed toxicity thus far in subjects taking ibrutinib for up to 7 days. Therefore, we can justify using the higher dose of 560 mg orally once daily for Part 2 to investigate whether this higher dose can further reduce skin test responses beyond what is seen with the lower dose.

In human studies, ibrutinib is metabolized in the liver, and not significantly renally cleared. In healthy volunteers, co-administration with CYP3A inhibitors increased Cmax, and therefore the drug will not be concomitantly administered with strong or moderate inhibitors of CYP3A. Known toxicities in cancer subjects receiving ibrutinib chronically include bleeding events (5% of MCL subjects), infection (25% of MCL subjects), myelosuppression (41% of subjects), and renal toxicity has also been reported. Ibrutinib is also pregnancy category D. This underscores our goal of finding the fewest possible doses to achieve the anti-allergy effect we are seeking, which could be as few as just 2 doses.

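### The section 10.2 power statement describes a 12-subject skin-test contrast that mixes two regimens, and its 80% fits neither 12 subjects (about 99.99%) nor the 6 per part (77.6%)

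*Combined protocol and SAP*

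**What the plan says.** Section 10.2 contains the only power statement and names the only statistical test in the plan: "12 subjects allows 80% power to detect a reduction in skin test positivity rate from 100% before treatment to 15% after treatment", with a McNemar test "using a one-sided 0.05 level". It does not mention the two parts or the two doses.

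Section 4.1 gives the make-up of the 12. For the first six: "For Part 1, 6 subjects will take ibrutinib 420 mg, by mouth once daily (every 24 hours) on an outpatient basis". They are tested after 2 doses, and dosing continues to 4 and then 7 doses while the tests have not turned negative. For the other six: "For Part 2 of the study, 6 subjects will take ibrutinib 560 mg once daily by mouth (every 24 hours) for 2 days". The Study Summary and section 10.1 confirm a total of 12 for the whole study.

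Section 1.2 gives a reason for the 560 mg dose in Part 2: "to investigate whether this higher dose can further reduce skin test responses beyond what is seen with the lower dose".

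Section 10.3 plans descriptive statistics, with each subject compared with his or her own baseline. It lists skin-test size for both parts and the food-challenge threshold for Part 2. It does not say whether the parts are summarised separately or together.

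**The concern.** With 6 subjects per part, 12 pairs exist only if both regimens are put into one table. The after-treatment result then means up to 7 doses of 420 mg in half the subjects, with up to three chances to convert, and 2 doses of 560 mg in the other half, with one fixed test. The combined conversion rate is an average over two exposures. It is not the effect of either, and it removes the difference that section 1.2 sets out to investigate.

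Two things are at stake. First, the figure that justifies the sample size describes no group given one regimen, so readers do not learn what 6 subjects per regimen can show. Second, if the 10.2 contrast were run as worded, one part alone could make it significant, and a single pooled statement about skin-test suppression would not show which regimen produced it.

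**Working it through.** **Inputs.** From 10.2: n = 12, stated power 80%, positivity "from 100% before treatment to 15% after treatment", one-sided 0.05, McNemar (version not stated). From 4.1: 6 + 6 subjects. From 3.1.3: a positive skin test is required at entry. A conversion here means a skin test that goes from positive to negative.

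**Rejection rule.** All subjects are positive at baseline, so discordant pairs can go only from positive to negative. With b conversions the exact one-sided p-value is 0.5^b:
- b = 4: p = 0.0625, not significant
- b = 5: p = 0.03125, significant
- b = 6: p = 0.0156, significant

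The test therefore rejects at b ≥ 5, whatever the number of subjects.

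**The plan's own figure.** The conversion probability is 1 − 0.15 = 0.85.
- n = 12: P(Bin(12, 0.85) ≥ 5) = 0.99993, about 99.99%.
- n = 6: P(Bin(6, 0.85) ≥ 5) = 6 × 0.85^5 × 0.15 + 0.85^6 = 0.3993 + 0.3771 = 0.776.

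The stated 80% is not reproduced. At n = 12 the other versions (mid-p, asymptotic, two-sided) also exceed 99.9%. With the exact one-sided test, 12 subjects have 80% power when positivity after treatment is about 50%, not 15%.

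**Version of the test at n = 6.** The power at 85% conversion depends strongly on the version:

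| Version | Conversions needed | Power, n = 6 |
|---|---|---|
| Exact one-sided | 5 | 77.6% |
| Mid-p one-sided | 4 | 95.3% |
| Asymptotic one-sided | 3 | 99.4% |
| Exact two-sided | 6 | 37.7% |

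The probability that both parts reach significance with the exact one-sided test is 0.776² = 60.3%.

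**Can one part carry the 12-pair contrast?** Let b = Bin(6, q1) + Bin(6, q2), where q1 and q2 are the conversion rates in the two parts. P(b ≥ 5) is:

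| q1 | q2 | Pooled test significant |
|---|---|---|
| 0.85 | 0 | 77.6% |
| 0.85 | 0.05 | 82.5% |
| 0.85 | 0.15 | 89.6% |
| 0.70 | 0 | 42.0% |
| 0.80 | 0 | 65.5% |
| 0.90 | 0 | 88.6% |

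The values are the same with the parts exchanged. With the asymptotic version (3 conversions enough), the first row becomes 99.4%.

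**What each presentation shows.** Suppose 6/6 convert in one part and 0/6 in the other. Exact 95% intervals:
- pooled: 6/12 = 50% (21% to 79%), p = 0.016
- one part: 6/6 = 100%, lower limit 0.025^(1/6) = 54%
- other part: 0/6 = 0%, upper limit 1 − 0.025^(1/6) = 46%

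The two separate intervals do not overlap, and the pooled interval describes neither part.

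**The case against.** The strongest reply is that no pooled test is planned. McNemar appears once, in the sample-size sentence. Section 10.3 is descriptive, compares subjects with themselves and tags the skin test with both parts, and a careful by-part description would show a part with no conversions. This stands. Pooling is inferred from 12 = 6 + 6, and the plan contains no decision rule that must mislead. What remains is that 10.2 bases the sample size on this contrast, and 10.3 does not require results by part.

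Four stronger readings are tempting, and the documents do not support them.

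- A reader might infer that the plan expects the doses to differ, or that 560 mg could plausibly do nothing. Section 1.2 poses a question, in the direction of more suppression at 560 mg, and reports at least partial inhibition after two 420 mg doses. The 85% and 0% scenario is an illustrative extreme.
- A reader might equate no conversions with no effect. Sections 10.0 and 10.3 also assess wheal size, which can shrink substantially without the test turning negative.
- A reader might make the Part 2 skin test decisive for the primary objective. Under sections 2.1 and 2.3 the primary endpoint is the food-challenge threshold, which no skin-test contrast tests. The Study Summary words the primary objective differently, but there the skin-test question is tied to 420 mg.
- A reader might infer that 80% was meant for one part of 6, since 77.6% is close. Section 10.2 says 12, and nothing in the documents shows how the 80% was obtained.

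**Conclusion.** The point holds as a defect in the sample-size justification, together with an analysis left unspecified. The 12-subject contrast combines two regimens and estimates neither. Its stated 80% power does not follow from its own inputs: about 99.99% with 12 subjects and 77.6% with the 6 who share a dose. If the contrast were run, 5 conversions in one part would make it significant with none in the other, with probability 77.6% at 85% and 0% conversion.

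These figures assume the exact one-sided McNemar test, every subject positive at baseline, independent subjects, and 12 different people (which follows from the stated total, not from an explicit sentence). The conclusion that 80% is wrong for 12 subjects does not depend on the version of the test; the 77.6% for 6 subjects does. The documents do not support the claim that the plan commits to a pooled test, or that a part without conversions shows no drug effect.

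**What to change.** **Section 10.2.** Replace the 12-subject statement with one for each part: 6 subjects, exact one-sided 0.05 McNemar test, 5 or more of 6 conversions needed, about 78% power for positivity falling from 100% to 15%. State which visit counts as after treatment in Part 1, where it could be the test after 2, 4 or 7 doses. In Part 2 it is Visit 2.

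**Section 10.3.** Report skin-test conversions separately for each part as x/6 with an exact 95% interval, next to the change in wheal size. Label any pooled 12-subject figure and any 420 mg versus 560 mg comparison as exploratory. Do not name the Part 2 skin test as decisive for the primary objective.

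**Cost.** Wording in two sections, with no added subjects or procedures. Intervals are wider, because each rests on 6 subjects and not 12. The stated power moves only from 80% to about 78%, but the authors should know that the actual power for the contrast falls from about 99.99% pooled to 77.6% per part.
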